## **5 BACKGROUND AND RATIONALE**

### **5.1 Background on Condition, Disease, or Other Primary Study Focus**

The advanced stage of Alzheimer's disease and other dementias is characterized by the onset infections, which prior work suggests are widely mismanaged. Antimicrobials are extensively prescribed, most often without evidence to support a bacterial infection. Antimicrobial exposure is the main factor leading to multidrug-resistant organisms (MDROs); a growing public health threat. Moreover, the benefits of antimicrobials remain unclear for patients with advanced dementia, for whom infections are often a terminal event and comfort is most commonly the goal of care.

In 2015, our group completed the **Study of Pathogen Resistance and Exposure to Antimicrobials in Dementia (SPREAD)** which prospectively examined antimicrobial use and MDRO acquisition in 363 NH residents with advanced dementia. Antimicrobials were prescribed for 72% of suspected infections, but only 44% of these episodes met guideline-based criteria for treatment. Suspected urinary tract (UTIs) and lower respiratory tract (LRIs) accounted for 94% of mistreated episodes. Criteria were more likely to be met when the residents' proxies were counseled about antimicrobials. Two-thirds of residents were colonized with MDROs. Antimicrobial use was the major risk factor for MDRO acquisition. Motivated by these findings, we conducted a pilot study (NIH R21) of a multi-faceted intervention to improve management of suspected UTIs and LRIs. Unlike standard NH antimicrobial stewardship programs, The intervention merged best practices in infectious diseases and palliative care, and targeted this unique population for whom the need and opportunity to improve infection management are particularly compelling.

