### 5.1.3 Benefits and burdens of treatment

Two potential benefits may motivate treating suspected infections in advanced dementia; prolonging life and symptom relief. In the absence of RCTs, observational studies help inform decision-making regarding these outcomes. In CASCADE, residents with pneumonia

treated with antimicrobials lived longer, but had more discomfort, than those who were not treated. In SPREAD, treating suspected UTIs with antimicrobials had no effect on survival. Both the work-up and treatment of infections can be burdensome for these frail patients. In SPREAD, 74% of suspected infections involved a bladder catheterization, hospital transfer, blood draw, or chest x-ray. Infections are the most common reason advanced dementia patients are hospitalized but can often be managed with similar efficacy in the NH. Even oral antimicrobials may cause discomfort, as these patients often have swallowing problems. Finally, older patients are more susceptible to adverse effects of antimicrobials such as *Clostridium difficile* infections, allergic reactions, MDRO acquisition, and drug-drug interactions.

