### **9.2 Resident assessments**

Resident data will be collected by RAs masked to the study arms. All data will be obtained from the residents' charts except for functional status and proxy ability to communicate in English, which will be ascertained in a 1-minute nurse interview. Data is collected from the medical records of enrolled residents every 2 months for up to 12 months, unless the resident passes or the proxy requests to opt out during that time. Their charts are abstracted at baseline, q2months, and within 30 days of death to determine whether antimicrobials were prescribed. If a treated episode was a suspected LRI or UTI, documented signs/symptoms will be ascertained to assess whether minimal criteria to start antimicrobials were present. Procedures used to evaluate these episodes (chest x-rays, bladder catheterization, blood draws, hospital transfer), and documented advance care planning about infection management (provider/proxy discussions and advance directives to withhold antimicrobials) will also be collected. A 1-minute nurse interview at baseline will also be done to assess the resident's functional status.

Demographic: (baseline) age, gender, race, ethnicity, length of NH stay, residing in a special care dementia unit, and proxy contact information (for mailing booklet) and relationship to resident.

Medical co-morbidity: (baseline) All active medical diagnoses.

Functional status: (baseline; nurse) Bedford Alzheimer's Nursing Severity-Subscale (BANS range, 7-28; higher score worse disability)

Antimicrobial exposure: (q2months, death) While analyses focus on treatment of suspected LRIs and UTIs, details about all antimicrobial courses will be ascertained from the medication administration records, including; suspected diagnoses, administration dates, agent, dose, route,

and prescribing provider. There are many ways to quantify antimicrobial exposure. We chose number of courses/person-years as our primary outcome as it best captures the intent of the intervention which is to reduce antimicrobial initiation. A course will be defined as starting an antimicrobial after a > 3-day treatment-free interval. Multiple antimicrobials given simultaneously for an episode will be considered single course for analytic purposes. For descriptive purposes, we will also quantify antimicrobial exposure as days of therapy (DOT)/person-days.

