Treated suspected UTIs and LRIs: (q2months, death): Documented details will be collected for treated suspected UTIs and LRIs, including: i. vital signs, mental status changes, localized signs and symptoms (e.g., lung sounds, cough, hematuria), ii. procedures used to evaluate including bladder catheterizations, chest x-rays, blood draws, iii. hospital transfer (admission or emergency room (ER), and vi. treatment discussions between providers and proxies. Signs and symptoms will be used to determine whether minimal criteria to initiate antimicrobials were met as operationalized in SPREAD and the pilot study.

Advance care planning: (baseline, q2months, death). The occurrence and date of advance care planning events will be ascertained from all available documentation (e.g., progress notes physician orders, POLST forms) and will include: discussions between providers and proxies about infection management and new directives to withhold antimicrobials (intravenous, intramuscular and/or oral) will be ascertained. Do-not-resuscitate and do-not-hospitalize orders will also be collected for descriptive purposes.

Devices: (baseline, q2months, death) feeding tubes, foley catheters

Health services: (q2months, death) hospitalizations, emergency room visits, hospice enrollment. 3.C.vii.1.i.

Other major new acute illnesses: (q2months, death), e.g. fracture, stroke, seizures. Death: RAs will phone the NH (nursing units) q2month.

Death date will be obtained from the chart.

Data Collection Elements and Protocol			
Data Collected	Purpose	From	When
Eligibility Screen			
Age, length of NH stay, available proxy	Eligibility	Chart	Screen
Advanced dementia	Eligibility	Nurse, Chart	Screen
IF ELIGIBLE			
Resident Characteristics			
Demographic, medical comorbidity, functional status	Descriptive	Chart	Baseline
Antimicrobial exposure			
Total courses for LRIs and UTIs 	1 o Outcome (Aim 1)	Chart, MAR 	q2months, death
Total courses for LRIs and UTIs  not meeting minimal criteria	2 o Outcome (Aim 2)	Chart, MAR 	q2months, death
Burdensome procedures to evaluate suspected LRIs and UTIs	2 o Outcome (Aim 3)	Chart	q2months, death
Advance care planning	2 o Outcome (Aim 3)	Chart	Baseline, q2months, death
Devices	Descriptive	Chart	Baseline, q2months, death
Health services utilization, new acute illnesses	Descriptive	Chart	q2months, death

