### 9.2.3 Follow-up Visits

Follow up chart reviews will be completed every 2 months for up to 1 year or until the resident dies. If the resident dies during the 12 month follow up period, a post-death chart review will be conducted. Follow-up chart reviews include the following elements:

- Demographics
- Advance directives
- Treatments/Investigations
- Healthcare utilization
- Sentinel Events
- Infection Screen

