## **10 HUMAN SUBJECT PROTECTIONS**

### **10.1 Sources of Data**

Residents' NH record: The residents' medical record containing information collected for routine clinical care will be abstracted at the baseline, q 2month and death assessments for up to 12 months. The following information will be obtained from the chart: demographic information, antimicrobial exposure and prescribing provider, lower respiratory and urinary tract episodes, medical comorbidity, advance care planning, devices, health care utilization, acute medical illnesses, and death date.

Nurse interviews: During screening procedures, nurses will be asked to identify subjects who meet criteria for Global Deterioration Stage 7. For enrolled residents, at baseline only, nurses will be asked to rate the functional status of the patients using the Bedford Alzheimer's Nursing Severity-Subscale during a 1-minute interview.

On-line course: Individual provider completion of the on-line course will be tracked.

NH residents, proxies, and NH providers (intervention arm only) will be assigned a study number known only to the co-principal investigators (PIs) and research assistants (RAs). NH providers in the intervention arm will be given a unique username and password to access the on-line education course known only to them, the PIs and project director. All documentation will

be stored in a locked area, accessible only to the PIs, RAs, and data manager. Data will be stored on computer workstations, accessible only through use of a unique password. Access to these data will be limited to study personnel on a “need to know” basis.

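### The Protocol 9.2 narrative ties collection of work-up procedures to treated suspected UTIs and LRIs, whereas outcome H3b counts them for suspected UTIs and LRIs with no treatment condition

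*Protocol*

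**What the plan says.** **Outcome.** Protocol 2.5 and 4.2 and SAP 1.2 and 3.5 (Aim 3) define H3b as the number of bladder catheterizations, blood draws, chest x-rays and hospital transfers used to evaluate suspected UTIs and LRIs. None of them requires that an antimicrobial was started.

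**Collection, narrative of Protocol 9.2.** Chart abstraction is introduced as a way of finding out whether antimicrobials were prescribed. The text continues: "If a treated episode was a suspected LRI or UTI, documented signs/symptoms will be ascertained". The next sentence covers "Procedures used to evaluate these episodes (chest x-rays, bladder catheterization, blood draws, hospital transfer", where the episodes meant are the treated ones just mentioned. The later item headed with the word treated repeats the limit: "Documented details will be collected for treated suspected UTIs and LRIs". Catheterizations, chest x-rays, blood draws and hospital transfer are among those details.

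**Collection, table in Protocol 9.2.** The row for this outcome reads "Burdensome procedures to evaluate suspected LRIs and UTIs", with no mention of treatment.

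**Collection, elsewhere.** Protocol 13.4.2 opens the UTI and LRI modules when such an infection is recorded at the infection screen. Protocol 9.2.2 to 9.2.4 list that screen at baseline, follow-up and post-death review. Protocol 9.2.3 and 9.2.4 also list "Treatments/Investigations" and healthcare utilization. Protocol 10.1 names "lower respiratory and urinary tract episodes, medical comorbidity, advance care planning" separately from antimicrobial exposure.

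**The concern.** The intervention is meant to lower antimicrobial initiation. Protocol 9.2 gives that as the reason for choosing courses as the primary outcome. If a procedure enters the episode data only when its episode was treated, then whether H3b is recorded depends on the decision that the trial tries to change.

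A fall in recorded procedures could then have two sources. One is a real reduction in work-up, which Protocol 5.1.4 regards as reasonable when comfort is the goal. The other is that the same work-up is done but the episode is left untreated and so drops out of the count. Treated-only data cannot separate the two. Masked abstractors, intention-to-treat analysis and robust variance do not help, because the problem lies in what is recorded.

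One secondary outcome is at stake. H1 and H2 count antimicrobial courses and do not depend on untreated episodes.

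**Working it through.** **The plan's own figure.** SAP 1.8 assumes that 72% of courses fail minimal criteria and that these fall by 35%: 0.72 × 0.35 = 0.252, taken as 25%. Withholding adds 5%, for a total of 30%. Then 0.30 × 1.26 = 0.378, which agrees with the stated 0.38 courses per person-year. For H3b the SAP gives only a control rate of 3.25 per person-year and no effect size, so there is no H3b calculation to reproduce.

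**Illustration under treated-only capture.** Assumptions: the same number of suspected episodes in both arms, one course per treated episode, and unchanged procedures per treated episode.

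- r = relative fall in courses = 0.30 (SAP 1.8)
- w = share of averted-course episodes still worked up as before (not in the documents; range 0 to 1)
- T = control-arm procedure rate in episodes that usual care treats
- U = procedure rate in episodes that usual care leaves untreated, taken as equal in both arms (not in the documents)

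Recorded ratio = T(1 − r) / T = 1 − r = 0.70, whatever w and U are.

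True ratio = [T(1 − r) + T·r·w + U] / (T + U) = 1 − r(1 − w) × T/(T + U).

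Because T/(T + U) cannot exceed 1, the true ratio lies between 0.70 and 1.00. With U = 0:

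| w | Recorded ratio | True ratio |
|---|---|---|
| 0 | 0.70 | 1 − 0.30 × 1.0 = 0.70 |
| 0.5 | 0.70 | 1 − 0.30 × 0.5 = 0.85 |
| 1 | 0.70 | 1 − 0 = 1.00 |

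A positive U moves the true ratio further towards 1. The size of that shift depends on how intensively untreated episodes are worked up, which the documents do not give. If only the 5% withholding effect occurred, the recorded ratio would be 0.95 and the true ratio between 0.95 and 1.00.

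**What the prior cohort can say.** Protocol 5.1.3 reports "In SPREAD, 74% of suspected infections involved a bladder catheterization, hospital transfer, blood draw, or chest x-ray", and Protocol 5.1 reports "Antimicrobials were prescribed for 72% of suspected infections". Both figures cover all infection types, and a shared denominator is an assumption. On that assumption, the share worked up but not treated is at least 0.74 − 0.72 = 0.02 and at most min(0.74, 1 − 0.72) = 0.28. As a share of worked-up infections this is 0.02/0.74 = 3% to 0.28/0.74 = 38%. These margins do not show whether the gap is small or large.

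**The case against.** The best reply is that the narrative is loosely worded and that practice was wider. Section 9.2 does not state one rule, since its own table omits the treatment condition. The form trigger in 13.4.2 is an infection recorded at screening, not a prescription. Protocol 11.1 and SAP 3.3 speak of collecting rates of suspected infections as well as their treatment. SAP 3.5 (Aim 1) likewise distinguishes suspected infections from the courses associated with them. Hospitalizations and emergency room visits are also collected separately under health services in 9.2.

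Much of this stands. It makes broader capture plausible, and it leaves hospital transfers less exposed than the other three procedures, although the health-services item is descriptive and has no stated link to a suspected UTI or LRI. It does not settle the matter. No section defines what counts as recorded at the infection screen or says that untreated suspected episodes are included. Nor does any section say that the investigation items in 9.2.3 and 9.2.4 feed H3b or carry an indication.

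Three stronger readings are tempting, and the documents do not support them:

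- **That data were lost and H3b is biased.** Nothing shows that untreated episodes were omitted.
- **That the gap must be substantial because 74% exceeds or nearly matches 72%.** Those margins allow as little as 2% of suspected infections to be worked up but untreated.
- **That the number of missed procedures can be calculated.** This would require reading 3.25 per person-year as a rate in treated episodes, and SAP 1.8 sets no such limit.

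**Conclusion.** The inconsistency is in the text and is unresolved. The 9.2 narrative collects procedures for treated suspected UTIs and LRIs, while H3b and the 9.2 table row carry no treatment condition. Confidence in this mismatch is high. Whether any procedures went uncounted cannot be judged from the documents.

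The consequence is conditional. If the narrative is followed, a recorded ratio of 0.70 is compatible with any true ratio from 0.70 to 1.00, given a 30% fall in courses and unchanged procedures per treated episode. Under those assumptions the distortion favours the intervention. If the mix of treated episodes also shifts, the direction is not known. The distortion is zero if the modules already capture untreated episodes or if untreated episodes receive no work-up.

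This should be fixed because the stated rule can give a wrong result for a named secondary outcome and the repair is specific and cheap. It does not touch the primary outcome.

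**What to change.** Reconcile the 9.2 narrative with its own table, with 13.4.2 and with SAP 3.5. State in 9.2, and in one sentence of the SAP, that procedures are abstracted for every suspected UTI or LRI found at the infection screen, whether or not an antimicrobial was started. If that was already the practice, only the 9.2 wording needs correcting.

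If the rule is changed while abstraction is under way, apply it to charts already abstracted as well. Homes enter in waves three months apart (SAP 1.5), so a change applied only to later charts would make capture differ by wave.

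If abstraction was treated-only for all or part of the trial, label H3b as procedures in treated episodes and do not interpret it as reduced overall burden. Add a sensitivity analysis, not a replacement endpoint, from the investigation and healthcare-utilization items in 9.2.3 and 9.2.4 where the data allow.

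The cost is a wording change and one SAP sentence, plus slightly longer abstraction of charts that are already read every two months, or re-abstraction of earlier charts. The sensitivity analysis would include procedures unrelated to infection, which would dilute any effect.

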### 9.2.1 Consenting Procedure (also see sections 7 and 16.2)

In accordance with federal guidelines, the HSL IRB granted a waiver of informed consent for the participation of both providers and residents (i.e., from proxies) based on: i. The determination of minimal risk, ii. The trial could not be practically conducted without the waiver. The NH is the unit of randomization and the intervention will be implemented as a new program for all advanced dementia residents. Including all eligible residents (versus only those consenting) reflects how the intervention would be used in the “real-world,” thus enhances the trial’s generalizability and interpretability, and iii. The trial does not adversely affect the rights and welfare of the subjects. Providers and proxies will have the opportunity to opt out at the start and throughout the implementation period, as described in Section 7.

### 9.2.2 Baseline Assessments

The charts of all eligible residents will be including in the baseline data abstraction unless the proxy has contacted the study team with a request for exclusion. Baseline assessments are chart review and data extraction along with a 1 minutes Bedford Alzheimer’s Nursing Severity-Subscale (BANS) interview to assess residents functional status. Baseline assessment includes the following:

- Demographics
- Health status
- Chronic or co-morbidities
- Advanced directives
- Recent history of treatments or investigations
- Healthcare utilization
- BANS interview
- Infection Screen

### 9.2.3 Follow-up Visits

Follow up chart reviews will be completed every 2 months for up to 1 year or until the resident dies. If the resident dies during the 12 month follow up period, a post-death chart review will be conducted. Follow-up chart reviews include the following elements:

- Demographics
- Advance directives
- Treatments/Investigations
- Healthcare utilization
- Sentinel Events
- Infection Screen

### 9.2.4 Post death Chart review

Post death chart reviews will be conducted within 30 days of enrolled residents passing. The research nurse will access the residents chart in the same way as she did for follow up chart reviews and collect the following information:

- Advance directives
- Treatments/Investigations
- Healthcare utilization
- Sentinel events
- Infection Screen

## **10 HUMAN SUBJECT PROTECTIONS**

### **10.1 Sources of Data**

Residents' NH record: The residents' medical record containing information collected for routine clinical care will be abstracted at the baseline, q 2month and death assessments for up to 12 months. The following information will be obtained from the chart: demographic information, antimicrobial exposure and prescribing provider, lower respiratory and urinary tract episodes, medical comorbidity, advance care planning, devices, health care utilization, acute medical illnesses, and death date.

Nurse interviews: During screening procedures, nurses will be asked to identify subjects who meet criteria for Global Deterioration Stage 7. For enrolled residents, at baseline only, nurses will be asked to rate the functional status of the patients using the Bedford Alzheimer's Nursing Severity-Subscale during a 1-minute interview.

On-line course: Individual provider completion of the on-line course will be tracked.

NH residents, proxies, and NH providers (intervention arm only) will be assigned a study number known only to the co-principal investigators (PIs) and research assistants (RAs). NH providers in the intervention arm will be given a unique username and password to access the on-line education course known only to them, the PIs and project director. All documentation will

be stored in a locked area, accessible only to the PIs, RAs, and data manager. Data will be stored on computer workstations, accessible only through use of a unique password. Access to these data will be limited to study personnel on a “need to know” basis.

## **11 POTENTIAL RISKS OF STUDY PROCEDURES**

The study meets criteria for minimal risk. All the resident data will be obtained from their medical record and nursing interviews, and coded at the time of data entry to protect their confidentiality. The residents in the control NHs will receive usual care for suspected infections. Residents in the intervention arm will receive care for the suspected infections at the discretion of their primary care providers as guided by the practice intervention. Given that the intervention is based on consensus, peer reviewed guidelines, the risk from the intervention with regards to infection management is minimal.

### **11.1 Potential Medial Risk to Study Participants**

Patients with advanced dementia are very frail. In the natural course of the disease, we expect of 40% mortality rate over one year. Thus, while deaths will be reported to the Data Safety Monitor, they are not considered an adverse event. The intervention does not involve any direct treatment of residents. Treatment of suspected infections is ultimately at the discretion of the nursing home primary care provider. Nonetheless, as part of this study, every 2 months, we will be collecting data from the residents’ charts about the rates of suspected urinary and respiratory infections, treatment of these infections, and appropriateness of that treatments as defined by our primary outcome.

### **11.2 Potential psychosocial (non-medical) risks, discomforts, inconveniences of study procedures**

We do not anticipate any potential psycho-social risks discomforts or inconveniences of study procedures beyond those encountered in usual care practices. The intervention provides information for proxies about infections in advanced dementia residents to promote informed decision-making that it is concordant with preferences, which is also desired goal for high quality nursing home care. The intervention was very well-received with no adverse events in the pilot study. Thus, we believe the intervention does not incur any greater distress than usual practice. Second, data collection conforms to the definition of minimal risk. No direct input from the residents or proxies is needed to complete any data for this study. All resident data are already being collected as part of routine medical care with the exception of the 1-minute nursing interview at baseline to quantify the resident’s functional status for descriptive purposes. All resident data are entered into a password protected encrypted software system using unique study identifiers. The data sheet linking residents with unique study ids is maintained in a separate secure system location at the discretion of the study site champion.

One additional potential burden of this study is the time commitment of the NH staff to assist with eligible subject identification, which involves 1-minute baseline nursing interviews, and intervention implementation. We will make every effort to minimize staff burden. Staff at the ~60 facilities that have participated in our prior large studies that used similar methods to recruit residents with advanced dementia felt the procedures were not too onerous. Based on our experience, the baseline nursing interview to quantify functional status is expected to take ~1

minute to complete. It is unlikely this burden will fall on a single nurse. Every effort will be made to conduct these interviews at times that are convenient for the nurses. Some burden will be experienced by the TRAIN-AD site champion and 15-20 targeted providers/NH (12-16 nurses, 1-3 physicians, 0-3 NPs/PAs) in the 12 intervention NHs with respect to the time required for initial training, completion of the on-line education course, use of algorithms to guide antimicrobial initiation, and review of prescribing feedback reports. All training procedures will be done at the convenience of these providers. Their involvement is voluntary. Group seminars will be conducted twice the same day to reach various shifts, and 1:1 sessions will be arranged for providers unable to attend the group training. The on-line course can also be done at the providers' convenience.

